### 9.3.4. Other Analyse(s)

The MDG will be computed by  $AUC_{24}/24$  hour.

The  $AUC_{(0-4)}$  for glucose, insulin, glucagon and C-peptide will also be calculated.

HOMA-IR will be mathematically calculated using FPG and FPI values.

All exploratory PD endpoints related to glucose, insulin, C-peptide, glucagon, HbA1c, and HOMA-IR will be summarized descriptively by treatment, time point and day. Additional analyses or summaries of these endpoints will be detailed in the SAP. Analysis of exploratory endpoints may not be included in the CSR.

For body weight, absolute values, CFB, and percent CFB will be summarized descriptively by treatment and day where the set of summary statistics will include n, mean, median, SD, minimum, and the maximum.

CCI

Analysis of 4- $\beta$ -hydroxycholesterol/cholesterol levels in plasma samples, if performed, will not be reported in the CSR.

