

To assess the PD effect on body weight changes following multiple doses of PF-07081532, administered orally, in adult participants with T2DM inadequately controlled on metformin and, if enrolled, in non-diabetic participants with obesity.

	

CFB in body weight at all post-dose timepoints as specified in the SoA.

To further characterize plasma PK of PF-07081532 following multiple doses administered orally, in adult participants with inadequately controlled T2DM on metformin and, if enrolled, in non-diabetic participants with obesity.

	

Additional PF-07081532 plasma PK parameters following multiple dose administration including, as data permit: <math>AUC_{24}(\text{dn})</math>, <math>AUC_{\text{inf}}</math>, <math>AUC_{\text{last}}</math>, <math>C_{\text{av}}</math>, <math>CL/F</math>, <math>C_{\text{max}}(\text{dn})</math>, <math>C_{\text{min}}</math>, <math>R_{\text{ac}}</math>, <math>R_{\text{ac},C_{\text{max}}}</math>, <math>PTR</math>, <math>V_z/F</math>.

Estimands are not applicable.

\*not analyzed in non-diabetic population with obesity, if enrolled.

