**Figure 1. Sample Dosing Scheme**

If a participant does not tolerate dose increment to the next dose level, as determined by the investigator and with notification to the sponsor, the participant may be reverted to the previously tolerated dose level. Following this dose modification, 2 separate attempts at increasing the dose to the next dose level are permitted, per investigator discretion. If, per investigator assessment, unacceptable intolerance (eg, severe vomiting) occurs shortly following dose administration, the dose will not be re-administered on the same day, and the participant may resume dosing at the current dose level at the next scheduled dosing time. Participants whose dose level is tolerability-limited may continue in the study for the intended duration of their assigned cohort at their own individual MTD, as judged to be appropriate by the PI and sponsor.

The planned cohorts in the study (Cohorts 1-3) may be conducted concurrently, partially overlapping or sequentially. The sponsor may decide not to conduct all planned cohorts, if it is judged that study objectives have been met. Up to 3 additional cohorts may be enrolled if judged necessary to meet the study objectives. One or more of the study cohorts may be conducted in non-diabetic participants with obesity, see [Section 4.2.1](#) and [Section 5](#).

Determination of eligibility will occur within 28 days of randomization based on criteria including medical history, vital sign, ECG and laboratory parameters, as detailed in [Section 5](#). Participants deemed eligible will be admitted to the CRU 7 days prior to start of dosing (Day -7) and will remain on-site until at least Day 45, post first dose.

The treatment period with double-blind study intervention will be 42 days, with study drug administered once daily. The participants within a given cohort will be blinded to the study treatment (PF-07081532 versus placebo). Participants who discontinue prior to completion of the study may be replaced, at the discretion of the PI and sponsor.

Upon discharge from the CRU, participants will return to the CRU 7 to 14 days after the last administration of IP for an on-site follow-up visit. A further follow-up contact with participants will be conducted at least 28 days and up to 35 days after the last administration of IP; this contact may be done via a phone call.

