The total duration of the study from the Screening visit to the last follow-up visit will be approximately 16 weeks of which 52 days will be inpatient at the CRU, followed by a follow-up period of 4-5 weeks, post last dose.

The study will be conducted in the USA.

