### 4.2.4. Endpoints

Clinical safety laboratory tests, thorough assessments of vital signs and 12-lead ECGs, physical examinations, and AE monitoring will provide essential data to evaluate the safety and tolerability of PF-07081532. To supplement standard clinical safety laboratory tests, calcitonin, amylase, lipase, TSH, T4 and lipid panel will be assessed based on the study population and guided by data available on marketed GLP-1R agonists. In addition, TBA will be assessed, based on non-adverse findings in the nonclinical studies with PF-07081532 (see [Section 2.2.2](#) and the IB).

While GLP-1R agonists typically are not associated with hypoglycemia unless co-administered with anti-diabetic agents that can cause hypoglycemia (such as insulin or sulfonylureas), blood glucose concentrations will be monitored throughout the study via a glucometer at least once daily (pre-breakfast), and careful monitoring of symptomatic hypoglycemic AEs will be performed.

In an effort to reduce variability and better quantify any potential changes in heart rate and BP during the study, all measurements of ECG and vital signs (pulse and BP) will be collected in triplicate (except as noted in the [SoA](#)) and the mean values will be used for analysis at each time point.

The effect of PF-07081532 on glucose response in participants with T2DM will be evaluated by determining the change from baseline in MDG. Since MDG is the time-averaged response over a day, it is expected that this glycemic parameter will be predictive of longer term glycemic control. The effect of PF-07081532 on body weight, FPG and other glycemic markers including insulin, C-peptide, HbA1c, and glucagon will also be assessed. FPG and FPI levels will be assessed and used to calculate HOMA-IR. In order to reduce variability in FPI for HOMA-IR calculation, triplicate measurements will be collected as indicated in the [SoA](#) and [Section 8.9.2](#). In an effort to reduce variability, minimize any potential effect of placebo or CRU confinement and better quantify any potential changes to these parameters, the participants will be admitted to the CRU on Day -7 in order to monitor compliance with background metformin and recommended diet.

Baseline (Day -1) assessments with time-matched procedures will permit within participant comparisons, as appropriate. In addition, placebo-adjusted (between participant) comparisons of dose-response will also be conducted.

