### 5.3.1. Meals and Dietary Restrictions

- Participants must abstain from all food and drink (except water) at least 8 hours prior to the blood sample collection at the outpatient **Screening** and on-site **follow-up** visits.
- Participants are required to fast for 4 hours (except water) prior to **admission** to CRU.
- Participants must abstain from all food and drink (except water) at least 8 hours prior to the first blood sample on inpatient study days [eg, for FSBG, safety laboratory, PK, or PD assessment].
- Noncaffeinated drinks (except as indicated below) may be consumed with meals and the evening snack.
  - Participants will refrain from consuming red wine, grapefruit, or grapefruit-related citrus fruits (eg, Seville oranges, pomelos, grapefruit juices) from 7 days prior to the first dose of investigational product until collection of the final PK blood sample.
- The initial caloric intake/menu assigned to each participant will be based on the Harris Benedict formula (sedentary lifestyle; to be provided to the site prior to study start) using the participant's body weight measured at screening.
- **Breakfast** will be provided at approximately 0800 hours on each inpatient day:
  - A standard breakfast will be provided for consumption after dosing on all days except those when liquid meal (for MMTT) is administered;
  - On days where liquid meal is administered, in lieu of breakfast, the meal will be provided as 16 ounces of Ensure Plus® and will be administered as listed in the [SoA](#). The entire Ensure Plus® meal is to be consumed within 10 minutes (See [Section 8.9.1](#)).
- **Lunch** will be provided approximately 4 hours after dosing (approximately 1200 hours) and at approximately the same time on each inpatient day. On days with liquid meal for breakfast, lunch will be provided after the 4-hour post-dose blood collection samples for the MMTT have been completed.
- **Dinner** will be provided approximately 10 hours after dosing (approximately 1800 hours) and at approximately the same time on each inpatient day.
- An **evening snack** may be permitted at approximately 2200 hours on non-MMTT days. On days when the MMTT is performed, an evening snack will be provided.
  - On days with MMTT as listed in the [SoA](#) (including the evening prior to MMTT) participants will be encouraged to consume all provided food, including the liquid

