3.3.6. Change from Baseline in Body Weight

Baseline for body weight will be defined as the pre-dose measure on Day 1. The change from baseline and percent change from baseline to all post-dose timepoints as specified in the schedule of activities will be calculated.

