6.4.2. Change from Baseline in Fasting Plasma Glucose, Fasting Plasma Insulin and HOMA-IR

- Estimand strategy: Not applicable
- Analysis set: Pharmacodynamic Population Set

Absolute values and change from baseline will be summarized descriptively by treatment and timepoint (when applicable) as described in [Section 5.2.1](#).

The change from baseline over time for FPG will be included in an MMRM model as described in [Section 5.2.3](#). The LSMMeans and LSMeans differences to placebo (with 90% confidence intervals) will also be plotted.

The change from baseline over time for FPI and HOMA-IR will be included in an ANCOVA model, as described in [Section 5.2.4](#), for each measure separately. The LSMeans and LSMean differences to placebo (with 90% confidence intervals) will also be plotted.

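### Body weight is the only retained PD endpoint with no planned difference from placebo, and its SAP baseline is a Day 1 weight that the visit schedule, as read, does not show

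*Protocol*

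**What the plan says.** **Objective.** Protocol Section 3 lists as exploratory: "To assess the PD effect on body weight changes following multiple doses of PF-07081532".

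**Setting.** Protocol 4.1 says that participants "will be admitted to the CRU 7 days prior to start of dosing (Day -7) and will remain on-site until at least Day 45", and gives a total duration of "approximately 16 weeks of which 52 days will be inpatient at the CRU". Protocol 5.3.1 adds: "The initial caloric intake/menu assigned to each participant will be based on the Harris Benedict formula".

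**Stated intent.** Protocol 4.2.4 lists body weight among the PD measures. It gives limiting placebo and confinement effects as one reason for admission on Day -7, and then states that "placebo-adjusted (between participant) comparisons of dose-response will also be conducted". It gives no method.

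**Planned analysis.** Protocol 9.3.4: "For body weight, absolute values, CFB, and percent CFB will be summarized descriptively by treatment and day". The same section makes the glucose, insulin, C-peptide, glucagon, HbA1c and HOMA-IR endpoints descriptive too, but defers further analyses of those to the SAP. Body weight has its own sentence with no such deferral.

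**SAP.** Section 3.3.6 derives change and percent change in weight and states: "Baseline for body weight will be defined as the pre-dose measure on Day 1". Section 3 otherwise sets baseline at Day -1. Section 6.4 runs from 6.4.1 to 6.4.4, in the contents list and in the text, with no body-weight entry. Its other subsections do model a placebo difference; for example, in 6.4.2, "The change from baseline over time for FPG will be included in an MMRM model".

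**The concern.** Change within one arm over 42 days of dosing in a residential unit combines any drug effect with whatever confinement and an assigned menu do to weight. Concurrent placebo participants are randomised and weighed on the same days, so the data to separate the two will exist. The plan does not say that the difference will be estimated, or with what uncertainty.

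A purely hypothetical case shows the stake. If placebo lost 1 to 2 kg and an active arm lost 3 kg, 33% to 67% of the active-arm change (1/3 to 2/3) would not be drug effect. The documents give no expected weight change for any arm.

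The baseline is a second, separate matter. If the day named in SAP 3.3.6 is not a weighing day, the derivation cannot be programmed as written and someone must choose a substitute, possibly after seeing data.

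**Working it through.** **1. Length of stay.** With no Day 0, Days -7 to -1 give 7 days and Days 1 to 45 give 45. 7 + 45 = 52, which reproduces the protocol's figure.

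**2. Which PD endpoints have a planned placebo difference?**

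| Endpoint | Placebo difference with 90% CI | Where |
|---|---|---|
| Insulin, glucagon, C-peptide AUC(0-4) | Yes, ANCOVA on log scale | SAP 6.4.1 |
| FPG | Yes, MMRM | SAP 6.4.2 |
| FPI, HOMA-IR | Yes, ANCOVA | SAP 6.4.2 |
| HbA1c | Yes, MMRM | SAP 6.4.3 |
| Glucose AUC(0-4), MDG | Withdrawn | SAP 2.1 |
| Body weight | None | no SAP 6.4 entry |

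The 4-beta-hydroxycholesterol ratio, which is not in the endpoint table, also gets a placebo difference (SAP 6.4.4). SAP 2.1 lists only the two glucose-based removals as departures from the protocol, so nothing says that a weight comparison was dropped.

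**3. Precision of the missing comparison.** Allocation is 9 active to 3 placebo per cohort (Protocol 4.1). The sample size is empirical (Protocol 9.5), so there is no power figure to reproduce. For a baseline-adjusted difference on one day, with complete data:

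half-width = t(0.95, df) × SD × √(1/n_active + 1/n_placebo)

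- Three T2DM cohorts, placebo pooled: 9 v 9, df = 36 − 4 groups − 1 covariate = 31. 1.696 × √(1/9 + 1/9) = 1.696 × 0.471 = 0.80 SD.
- One cohort alone: 9 v 3, df = 12 − 2 − 1 = 9. 1.833 × √(1/9 + 1/3) = 1.833 × 0.667 = 1.22 SD.

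The documents give no SD of weight change. For an assumed residual SD:

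| Assumed SD (kg) | 9 v 9 (± kg) | 9 v 3 (± kg) |
|---|---|---|
| 1.5 | 1.2 | 1.8 |
| 2.0 | 1.6 | 2.4 |
| 2.5 | 2.0 | 3.1 |

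**4. Is there a Day 1 weight?** Counting cells in Protocol Table 1, the body-weight marks fall at Screening, Day -7, Day -1, then Days 8, 14, 22 and 29, then later columns. The Day 1 cell is empty, and Table 2 has no weight row. The ECG row supports this alignment: its early marks fall on Day 2 (correct for the 24-hour reading after Day 1), then Days 8, 14, 22 and 29. Other parts of the table do drift. The first dosing mark falls under Days 3-7 although dosing starts on Day 1, and the 24-hour ECG mark after Day 42 falls under Day 45 instead of Day 43. An empty Day 1 cell is therefore probable, not certain.

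**5. Analysis set.** The PD population (Protocol Table 4, SAP Section 4) requires at least one dose of PF-07081532. Read literally, that excludes placebo participants, so an added contrast must name another set.

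**The case against.** The strongest reply is that descriptive reporting was a deliberate choice. The endpoint is exploratory, no hypothesis testing is planned (Protocol 9.1), the study is sized empirically for safety and tolerability, Protocol 4.3 says that doses need not reach efficacy targets, and Protocol 9.3.4 allows exploratory analyses to stay out of the study report. Summaries by treatment include placebo, with n, mean and SD, so an unadjusted difference and interval could be worked out by hand. The Day -7 admission is itself a mitigation, and Protocol 5.3.1 sets only the initial intake and does not require participants to finish standard meals on most days.

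Much of this stands. A reader might infer that the study cannot answer its weight objective; the documents do not support that, because the control data will be tabulated. Nor do they say that weight will move in every arm. A reader might also infer that weight is the only named PD endpoint without a contrast; that is not so, since MDG and glucose AUC(0-4) remain in the SAP 2.2 table after their analyses were withdrawn. The statement holds only for retained endpoints.

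The absence of testing does not settle the matter. The SAP gives blood pressure, pulse rate, QT, heart rate and QTcF treatment-minus-placebo differences with 90% CIs (6.2.1.6, 6.2.1.7), purely as estimation. A seven-day run-in cannot remove confinement effects that continue through dosing.

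Redacted text follows the body-weight sentence in Protocol 9.3.4, and SAP 6.6.3 is redacted. Relevant wording there cannot be excluded, although the 6.4 contents list is unbroken.

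**Conclusion.** The point holds as a gap between stated intent and planned analysis, on an exploratory endpoint. Protocol 4.2.4 says that placebo-adjusted comparisons will be made; neither Protocol 9.3.4 nor the visible SAP specifies one for body weight, while every other retained PD endpoint has one. What is missing is a baseline-adjusted difference and its interval, not the placebo data.

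How informative that interval would be depends on the cohorts run. The 0.8 SD figure needs three full T2DM cohorts. Protocol 4.1 allows fewer, and any obesity cohort has its own placebo group (SAP Section 6). With one cohort in a population the figure is 1.22 SD, which at an assumed SD of 2.5 kg is ± 3.1 kg. The kilogram figures rest entirely on assumed SDs.

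The baseline point is probable only. It is tempting to conclude that Day 1 weight was never collected and that every change value would come out missing. The table as read does not establish that, and SAP Section 3 allows endpoint-specific baselines. What is established is that SAP 3.3.6 departs from the SAP default and from Protocol 4.2.4, which also calls Day -1 baseline, and that it needs reconciling with the schedule. This is worth correcting in the SAP; it does not affect the primary or secondary objectives.

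**What to change.** 1. Add a body-weight subsection to SAP 6.4. Analyse change and percent change from baseline with the SAP 5.2.3 MMRM (treatment, baseline, day, baseline by day, day by treatment). Report LS mean differences from the placebo group of the same population, with 90% CIs, at each scheduled day, labelled as exploratory estimation. Keep the descriptive tables.
2. State that the 5.2.3 covariance fallback applies. Table 1 as read has about six post-dose weighings, so an unstructured matrix has 6 × 7 / 2 = 21 parameters, too many for a population with a single cohort of 12.
3. Use all dosed participants including placebo; the Full Analysis Set as defined does this. Do not use the PD population as worded.
4. Check Protocol Table 1. If a Day 1 predose weight is scheduled, keep SAP 3.3.6. If not, define baseline as the Day -1 weight, the last one scheduled before dosing.

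The cost is SAP wording and further runs of a model already planned for FPG and HbA1c. No new assessments are needed.

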#### **9.4. Interim Analyses**

No formal interim analysis will be conducted for this study. As this is a sponsor-open study, the sponsor may conduct unblinded reviews of the data during the course of the study for the purpose of safety assessment, facilitating dose selection decisions, facilitating PK/PD modeling, and/or supporting clinical development.

#### **9.5. Sample Size Determination**

A sufficient number of participants will be screened to achieve an estimated total of approximately 12 evaluable participants per cohort (9 PF-07081532:3 placebo).

The number of participants was selected empirically to provide a sufficient number of participants to assess and characterize the safety and tolerability of various doses and dosing schemes of PF-07081532.

## **10. SUPPORTING DOCUMENTATION AND OPERATIONAL CONSIDERATIONS**

### **10.1. Appendix 1: Regulatory, Ethical, and Study Oversight Considerations**

#### **10.1.1. Regulatory and Ethical Considerations**

This study will be conducted in accordance with the protocol and with the following:

- Consensus ethical principles derived from international guidelines, including the Declaration of Helsinki and CIOMS International Ethical Guidelines;
- Applicable ICH GCP guidelines;
- Applicable laws and regulations, including applicable privacy laws.

The protocol, protocol amendments, ICD, SRSD(s), and other relevant documents (eg, advertisements) must be reviewed and approved by the sponsor, submitted to an IRB/EC by the investigator, and reviewed and approved by the IRB/EC before the study is initiated.

Any amendments to the protocol will require IRB/EC approval before implementation of changes made to the study design, except for changes necessary to eliminate an immediate hazard to study participants.

Protocols and any substantial amendments to the protocol will require health authority approval prior to initiation except for changes necessary to eliminate an immediate hazard to study participants.

The investigator will be responsible for the following:

- Providing written summaries of the status of the study to the IRB/EC annually or more frequently in accordance with the requirements, policies, and procedures established by the IRB/EC;
- Notifying the IRB/EC of SAEs or other significant safety findings as required by IRB/EC procedures;
- Providing oversight of the conduct of the study at the site and adherence to requirements of 21 CFR, ICH GCP guidelines, the IRB/EC, European regulation 536/2014 for clinical studies (if applicable), European Medical Device Regulation 2017/745 for clinical device research (if applicable), and all other applicable local regulations.

##### **10.1.1.1. Reporting of Safety Issues and Serious Breaches of the Protocol or ICH GCP**

In the event of any prohibition or restriction imposed (ie, clinical hold) by an applicable regulatory authority in any area of the world, or if the investigator is aware of any new information that might influence the evaluation of the benefits and risks of the study intervention, Pfizer should be informed immediately.

In addition, the investigator will inform Pfizer immediately of any urgent safety measures taken by the investigator to protect the study participants against any immediate hazard, and of any serious breaches of this protocol or of the ICH GCP guidelines that the investigator becomes aware of.

### **10.1.2. Informed Consent Process**

The investigator or his/her representative will explain the nature of the study, including the risks and benefits, to the participant or his/her legally authorized representative and answer all questions regarding the study. The participant or his/her legally authorized representative should be given sufficient time and opportunity to ask questions and to decide whether or not to participate in the trial.

Participants must be informed that their participation is voluntary. Participants or their legally authorized representative will be required to sign a statement of informed consent that meets the requirements of 21 CFR 50, local regulations, ICH guidelines, privacy and data protection requirements, where applicable, and the IRB/EC or study center.

The investigator must ensure that each study participant or his or her legally authorized representative is fully informed about the nature and objectives of the study, the sharing of data related to the study, and possible risks associated with participation, including the risks associated with the processing of the participant's personal data.

The participant or his or her legally authorized representative must be informed that his/her personal study-related data will be used by the sponsor in accordance with local data protection law. The level of disclosure must also be explained to the participant or his or her legally authorized representative.

The participant or his or her legally authorized representative must be informed that his/her medical records may be examined by Clinical Quality Assurance auditors or other authorized personnel appointed by the sponsor, by appropriate IRB/EC members, and by inspectors from regulatory authorities.

The investigator further must ensure that each study participant or his or her legally authorized representative is fully informed about his or her right to access and correct his or her personal data and to withdraw consent for the processing of his or her personal data.

The medical record must include a statement that written informed consent was obtained before the participant was enrolled in the study and the date on which the written consent was obtained. The authorized person obtaining the informed consent must also sign the ICD.

Participants or his or her legally authorized representative must be re-consented to the most current version of the ICD(s) during their participation in the study.

A copy of the ICD(s) must be provided to the participant or the participant's legally authorized representative.

Participants who are rescreened are required to sign a new ICD.

